1.1 Background

Osteoporosis is a multi-factorial skeletal disease characterized by low bone mass and a structural deterioration of the macro and microarchitecture of bone tissue, leading to increased bone fragility and susceptibility to fracture [1]. Osteoporosis is considered a global public health concern, due to its prevalence worldwide. Yet its pathogenesis has not been clear. Osteoporosis affects numerous people, of both sexes and all races, and its prevalence increases as the population ages. Currently, it has been estimated that over 200 million people, including 75 million in the United States, Western Europe and Japan [2], have osteoporosis. Approximately 30% postmenopausal women are osteoporotic in the US and in Europe [2]. In China, an observational study has suggested a total of 54 million women aged 50 or above have osteoporosis, representing a prevalence of 27.3% in this affected population [3].

Osteoporosis is often called a 'silent disease'. Its diagnosis relies on a bone mineral density (BMD) value by dual-energy X-ray absorptiometry (DXA, DEXA) [1] and/or a proven fragility fracture at major skeletal sites [2, 3]. It has a significant clinical impact because of the association with an increased risk of fractures at major skeletal sites including the hip, the vertebrae, and the distal forearm. At least 40% of osteoporotic women [4] and 15-30% of men [5] experience one or more fragility fractures in their remaining lifetime. The combined lifetime risk of hip, forearm and vertebral fractures (VF) is 40%, being equivalent to the risk of cardiovascular diseases [6]. Moreover, an initial osteoporotic fracture by any type is a major risk factor for a new fracture [7, 8]. For instance, patients with a history of VF have a 2.3-fold increased risk of a future hip fracture and a 1.4-fold increase in risk of distal forearm fracture [8]. These fragility fractures lead to a substantial loss of quality of life [6, 9], an increased hospitalization [10, 11] and an excessive risk of mortality [12], and thus cause a tremendous socioeconomic burden. Currently, Chinese therapeutic guideline has recommended a routine screening program, consisting of blood chemistry, chest-waist spine radiology, and DXA, for the diagnosis and treatment of osteoporosis in various populations including postmenopausal women with or without other socioeconomic and/or clinical risks.

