2.2 Secondary Objective(s)

1. To investigate the prevalence of osteoporosis in community-dwelling postmenopausal women in China;
2. To identify risk factors for prevalent vertebral fractures in community-dwelling postmenopausal women in China;
3. To identify risk factors for densitometric osteoporosis in community-dwelling postmenopausal women in China.

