3.5 Stratification

The subjects will be sampled and stratified according to the following factors:

- 1) Age;

Seven (7) age groups: 50 - 54, 55 - 59, 60 - 64, 65 - 69, 70 - 74, 75 - 79, 80 or above;

- 2) Geographic region;

Five (5) regions in China: North, South, Southeast, Southwest, and Central

4 Variables and Epidemiological Measurements

All eligible participants will be included in the study to an endocrinologist, or other specialist, whenever appropriate, for the collection of all clinical and radiological information by 1 onsite study visit in a cross-sectional fashion. Spine radiograph and/or DXA may be separated from onsite interview by a follow-up visit as determined by the investigator.

Questionnaire

All demographic data, socioeconomic status, lifestyle information, and clinical features including medical history/concomitant medications, will be collected by an interviewer-administered questionnaire performed by the investigator. The questionnaire will be designed to adapt China's cultural and clinical practice. The analyzable variables derived from the questionnaire include (but not limited to):

- Age (absolute value and category);
- Place of birth and dwelling geographic region;
- BMI (height and weight, as measured in the site);
- Social status and lifestyle (educational level, occupation, monthly income, physical exercise, diet, smoking, alcohol intake, diet, calcium intake);
- Clinical features (age and years of menopause, medical history, history of osteoporosis and parental osteoporosis, any prior fractures, prior and concomitant medication, antiresorptive treatment, glucocorticoid treatment, other treatment reducing bone mass);
- FRAX score (as determined by self-reported fracture and radiology evidence and calculated based on the information from questionnaire with/without BMD).

BMD Measurement

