The subject's densitometric measurement will be performed by DXA onsite. Different DXA scanners from manufacturers including Hologic, Lunar and Norland will be used onsite upon availability. The BMD of three skeletal locations, the lumbar spine, the femoral neck, and the total hip, will be determined and presented as absolute value, T-score. The definitions of normal (≥ -1.0 SD compared to young adult women), osteopenia (between -1 to -2.5 SD compared to young adult women) and of osteoporosis (≤ -2.5 SD compared to young adult women) will be applied for both locations in the study, by assessing densitometric readings based on the World Health Organization(WHO)classification [41]. Reference databases for the calculation of the T-score include the National Health and Nutrition Examination Survey (NHANES) III database for the hip and the manufacturer's database for the spine [42]. The US reference database in DXA devices provided by the manufacturers has been adopted in local China's clinical practice [3] and validated in published Chinese studies [36, 39]. No

single local reference database will be applied for a recalculation of T-score due to its relatively smaller sample size and lack of an extensive validation across Asian populations.

DXA has been established as a reliable method providing acceptable precision and accuracy. For lumbar spine, coefficients of variation (CV) in measurements have been reported between 0.26 and 1.5% in short-term studies [43-46], and between 0.8 and 2.6% in long-term studies [43-46]. Precision results for spine phantom measurements using DXA were reported between 0.4 and 0.67% and in long-term studies between 0.23% and 1.0% [43, 45-47]. The DXA measurement for the lumbar spine has a satisfactory diagnostic profile in terms of sensitivity and specificity (ROC AUC 94%) [45].

DXA Quality Control

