8.1.2.2 Risk Factors for Radiographic Vertebral Fracture or Densitometric Osteoporosis

As secondary objectives, all possible factors including socioeconomic status, lifestyle and clinical parameters will be assessed to identify if they are the risk factors of a prevalent vertebral fracture or densitometric osteoporosis in Chinese postmenopausal women.

A two-step statistical modeling will be established to assess the potential risks against the response of analysis interest (dependent variable). Initially, a single logistic regression for bivariate analysis will be used to give a percentage tabulation presenting proportions of case (morphometric vertebral fracture or densitometric osteoporosis) versus control by each analysis parameter. An odds ratio and associated probability (P value) will be given to examine the statistical significance of this independent variable in the model. A P value of 0.25 or less will be the criterion [54] for an entry into a multivariate logistic model for all estimated variables. Also, all clinically relevant variables, regardless of a probability level, will be included in the final model at the discretion of the study team.

Finally, a multivariable logistic regression model will be constructed for both dependent variables. A stepwise backward method to eliminate non-significant variables will be performed until all remaining variables in the model have a P value less than 0.1. The goodness-of-the-fit will be evaluated by using deviance and likelihood ratio tests and Hosmer–Lemeshow test [55] to assess if there is any single important variable missing from the model.

In the bivariate and multivariate analysis, age, BMD, and BMI will be fitted as continuous variables. Geographic region grouping study sites will be fitted as a categorical variable. Due to potential collinearity of BMD to vertebral fracture, BMD will also be introduced as a dichotomous variable (osteoporosis vs. normal and osteopenia). BMI may vary among study sites in the study, odds ratio per unit BMI instead of per standard deviation to minimize the biases upward.

8.1.3 Exploratory Objective(s): Calculation of Epidemiological Measure(s) of Interest (e.g. hazard ratios, incidence rates, test/retest reliability)

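### No multivariable vertebral-fracture model without BMD is specified, so secondary objective 2 gets no adjusted estimate for factors that act through bone density

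*Combined protocol and SAP*

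**What the plan says.** Section 2.2 lists as secondary objective 2 "To identify risk factors for prevalent vertebral fractures in community-dwelling postmenopausal women in China" and as objective 3 "To identify risk factors for densitometric osteoporosis in community-dwelling postmenopausal women in China". Neither is restricted to effects that are independent of BMD.

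Section 8.1.2.2 serves both objectives in two steps. Each factor is first tested alone in a logistic regression and goes forward if P is 0.25 or less. A multivariable logistic model is then reduced backward until every remaining variable has P below 0.1. The study team may also include variables it judges clinically relevant whatever their P value, but no list is given.

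On coding, the section states: "In the bivariate and multivariate analysis, age, BMD, and BMI will be fitted as continuous variables". It continues: "Due to potential collinearity of BMD to vertebral fracture, BMD will also be introduced as a dichotomous variable (osteoporosis vs. normal and osteopenia". It does not say which coding gives the reported model, which of the three measured skeletal sites supplies BMD, or whether any multivariable fracture model omits BMD.

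Other sections place bone mass on the pathway to fracture. Section 1.1 describes osteoporosis as "characterized by low bone mass and a structural deterioration of the macro and microarchitecture of bone tissue, leading to increased bone fragility and susceptibility to", a sentence that closes on fracture. The questionnaire variables in Section 4 include "antiresorptive treatment, glucocorticoid treatment, other treatment reducing bone mass", alongside BMI, menopause, smoking and calcium intake.

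**The concern.** If a factor lowers bone density and low bone density causes fracture, BMD is a mediator. Conditioning on a mediator removes the part of the effect that passes through it. What remains is the BMD-independent effect, which may be close to nothing for a factor that matters a good deal. Elimination at P<0.1 then tends to take that factor out of the final model.

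The rationale for the dichotomous version does not help. Collinearity is a relation among predictors. A strong association between BMD and fracture is a relation between a predictor and the outcome, and is no reason to recode the predictor. Cutting BMD at the osteoporosis threshold controls for it incompletely, so part of the mediated effect returns to the other coefficients.

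At stake is the interpretation of secondary objective 2. A reader of the final fracture model could take a missing factor as one that does not raise fracture risk, when the model shows only that it adds little once BMD is known. The primary prevalence estimates are not affected. The point concerns the fracture model only, not the model for densitometric osteoporosis.

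**Working it through.** **Sample size used.** The age-group sizes in Table 8.3.1 sum to 44+81+100+90+80+70+53 = 518. Allowing for 5% loss of radiographs, 518/0.95 = 545.3, which reproduces the stated 545 per region. The total is about 2700, so 2700 × 0.95 = 2565 women have radiographs. The table's weighted mean prevalence is 85.98/518 = 16.6%. No figure in the plan is disputed; these only set the scale.

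**Approximation.** For a factor that shifts BMD by d, with fracture log odds ratio b per unit of BMD decrease and direct log odds ratio c:
- model without BMD: log OR ≈ c + d·b
- model with continuous BMD: log OR ≈ c

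With c = 0, d = 0.5 and b = ln 2, the first is 0.5 × 0.693 = 0.347, or OR 1.41. The second is 0, or OR 1.00.

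**Simulation A (BMI).** The effect sizes are assumptions, since the documents give none.
- N = 2565, Table 8.3.1 age mix, fracture prevalence about 16–17%, 1000 studies per scenario.
- BMI acts only through BMD: 0.25–0.35 SD of BMD per SD of BMI; fracture OR 1.5–1.8 per SD lower BMD.
- The models contain age and BMI, plus BMD where stated. The dichotomy is at the lowest 27.3% of BMD, the osteoporosis prevalence cited in Section 1.1.

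BMI was retained at P<0.1 in 56–98% of studies without BMD, 9–11% with continuous BMD and 18–43% with dichotomised BMD. At 0.25 SD and OR 1.8 the BMI odds ratios per SD were 0.87, 1.00 and 0.94. The approximation gives exp(−0.25 × ln 1.8) = exp(−0.147) = 0.86 without BMD, in agreement.

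**Simulation B (binary factor).** N = 2565, 600 studies per scenario, factor prevalence 20%. T-score = −1.6 − 0.45 per 10 years of age − d × factor + normal error (SD 1.05). Fracture log odds = −1.9 + 0.55 per 10 years of age − b × (T-score + 1.6) + c × factor. Age is centred at 67 and the dichotomy is at −2.5. All models are adjusted for age.

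| d | fracture OR per T-score unit | direct OR | no BMD: OR, retained | continuous BMD: OR, retained | dichotomised BMD: OR, retained |
|---|---|---|---|---|---|
| 0.3 | 1.5 | 1.0 | 1.12, 22% | 1.00, 10% | 1.05, 12% |
| 0.5 | 2.0 | 1.0 | 1.37, 79% | 1.00, 10% | 1.13, 24% |
| 0.8 | 2.0 | 1.0 | 1.65, 99% | 0.99, 13% | 1.20, 43% |
| 0.5 | 2.0 | 1.2 | 1.63, 98% | 1.20, 41% | 1.35, 77% |

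Over all six fully mediated scenarios, retention was 22–99% without BMD, 8–13% with continuous BMD and 12–43% with dichotomised BMD. With continuous BMD, a causal factor is kept about as often as noise (nominal 10%).

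The shift can also run the other way. A factor of prevalence 25% that raises the T-score by 0.4 (fracture OR 1.8 per unit) and has a direct OR of 1.3 was retained in 13% of studies without BMD, 62% with continuous BMD and 33% with dichotomised BMD. The models answer different questions.

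**The case against.** Several points on the other side stand.

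- **Fracture analyses free of BMD exist.** Each factor's bivariate odds ratio and P value are reported, so a reader might wrongly infer that every planned fracture analysis contains BMD. But those odds ratios are unadjusted, while the assumed fracture prevalence in Table 8.3.1 rises from 5% to 37% across the age groups.
- **There are other routes to a mediated factor.** It may appear in the densitometric-osteoporosis model, and the study team may force it into the fracture model. The former has a different outcome. The latter is discretionary and still yields a BMD-adjusted odds ratio.
- **Adjusting for BMD can be right.** Section 3.1 says the analyses will go on to a risk assessment model for vertebral fracture, where BMD belongs. BMD is also a candidate, not declared a forced term. The documents do not support a claim that BMD must be kept out; the gap is that the other model is missing.
- **The dichotomy is additional.** Section 8.1.2.2 keeps continuous BMD, so using the study's own diagnostic cut as a second look is tolerable if labelled.
- **The illustration is favourable to the concern.** Full mediation is the extreme case. The models hold few covariates and skip the P≤0.25 screen. In the weakest scenario the factor is dropped in 78% of studies even without BMD.
- **The data are cross-sectional.** BMD, BMI and treatment are recorded after any prevalent fracture, and antiresorptive treatment may follow one. A model without BMD still estimates associations.

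None of this supplies an age-adjusted, BMD-free estimate for objective 2. Section 8.1 announces a separate SAP, but defers no BMD rule to it.

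**Conclusion.** The point holds as an omission in a secondary analysis. Section 8.1.2.2 specifies no multivariable fracture model without BMD, gives a mistaken reason for dichotomising BMD, and leaves open which coding is reported. Under the assumed effects, a factor acting only through BMD falls from 56–98% retention (BMI) or 22–99% (binary factor) without BMD to roughly 10% with continuous BMD. The size depends on effect sizes the documents do not give. The direction was the same in every fully mediated scenario.

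Two stronger readings are not supported. One is that BMD coding decides the list of risk factors. Fully mediated factors are mostly dropped under either coding: 87–92% of studies with continuous BMD and 57–88% with dichotomised BMD in simulation B. Coding is the smaller problem and matters most for strong or partly direct factors, such as 41% against 77% in the last row of the table. The other is that a mediated factor will necessarily be reported as no risk factor. Elimination is a matter of probability, and the bivariate results remain on view.

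**What to change.** In Section 8.1.2.2, carried into the separate SAP:

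1. Pre-specify a multivariable fracture model that includes age and excludes BMD, and name it as the analysis for secondary objective 2.
2. Pre-specify a second fracture model that adds one named continuous BMD measure (for example femoral neck, for which Section 4 gives cross-calibration equations). Label its odds ratios as effects independent of BMD, and make it available for the risk assessment model in Section 3.1.
3. Delete the collinearity rationale. Drop the dichotomous BMD version or label it a sensitivity analysis.
4. Report both models as cross-sectional associations.

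The cost is a few sentences, one extra model run and a second column of odds ratios. No new data are needed. The P<0.1 elimination rule can stay, but it will still drop some real factors from the first model: in the weakest BMI scenario, 100% − 56% = 44% of studies.

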2.3 Exploratory Objective(s)

1. To assess the diagnostic accuracy of onsite radiology imaging for vertebral fractures in China's local clinical practice;
2. To assess the diagnostic role of vertebral imaging for the screening of osteoporosis and pharmacological treatment in China's local clinical practice.

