8.1 Statistical Methods

This section outlines the statistical analysis strategy and procedures for the study. If, after the study has begun, changes are made to primary and/or key secondary hypotheses, or the statistical methods related to those hypotheses, then the protocol will be amended. Changes to exploratory or other non-confirmatory analyses made after the protocol has been finalized, along with an explanation as to when and why they occurred, will be listed in the CSR for the study. Post hoc exploratory analyses will be clearly identified in the CSR. A separate SAP will be created for this study.

8.1.1 Primary Objective(s): Calculation of Epidemiological Measure(s) of Interest (e.g. descriptive statistics, hazard ratios, incidence rates, test/retest reliability)

The study's primary objective is to investigate the prevalence of radiographic vertebral fractures in community-dwelling postmenopausal women in China. Descriptive statistics will be made to statistically address this objective. No hypothesis testing will be applied in the study for this primary objective.

Point estimates (percentage) of prevalence by overall study population and by age group and/or geographic region will be calculated and displayed. A fracture case is defined and counted as the subject with the presence of at least one vertebra classified as grade 1, 2, or 3 semi-quantitatively by Genant's score as agreed by both study radiologists.

Point estimates of prevalence rates by overall and geographic region will be adjusted by a nationwide age distribution using the database from Basic Statistics on National Population Census 2010, National Bureau of Statistics of China [53]. A direct method of adjusting rates will be made to give age-standardized prevalence. Age-standardized rate by regional age distribution data may be calculated subject to site location and will be specified in the SAP before database lock and study analyses.

A corresponding two-sided 95% confidence interval (CI) for each individual point estimate will be given. This 95% CI is based on a direct calculation of the exact binomial distribution. A more conservative method, the Wilson Score CI [52], will be applied to give 95% CIs for all point estimates and compared with the exact binomial distribution.

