The diagnostic accuracy of onsite vertebral imaging will be tabulated by a simple 2*2 contingency table against blinded adjudication. Sensitivity, specificity, positive predictive value (PPV), negative predictive value (NPV), and likelihood ratio will be given with a corresponding 95% CI. Kappa test for inter-observer agreement between onsite and blinded experienced radiologists will be calculated and presented. Logistic regression model will also be used to assess the probability of a subject with adjudicated vertebral fracture will have the vertebral fracture as diagnosed onsite. The area under the Receiver Operating Characteristic (ROC) curve will be given to evaluate the degree of discrimination for the probability of interested response. Effects of age, region, and/or other analysis variables will be adjusted in the model whenever statistically appropriate.

Assessment in the diagnostic role of vertebral imaging for the screening of osteoporosis will be explored by a simple binary diagnostic test. An osteoporosis diagnosis in the study will be deemed as 'true condition' whereas the blinded vertebral imaging outcome will be the diagnostic tool. Sensitivity, specificity, PPV, NPV, and likelihood ratio will be presented with a corresponding 95% CI. Similarly, logistic regression model will also be used to assess the probability of a subject with adjudicated vertebral fracture will have densitometric osteoporosis. The area under the ROC curve will be given to evaluate the degree of discrimination for the probability of interested response. Effects of age, region, and/or other analysis variables will be adjusted in the model whenever statistically appropriate.

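### Section 8.1.3 attaches the AUC for exploratory objective 1 to a model whose response is the onsite diagnosis, so that AUC does not measure the accuracy of onsite reading

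*Combined protocol and SAP*

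**What the plan says.** Exploratory objective 1 (Section 2.3) is: "To assess the diagnostic accuracy of onsite radiology imaging for vertebral fractures in China's local clinical practice". The onsite reading is therefore the test under evaluation.

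Section 8.1.3 starts consistently with that: "The diagnostic accuracy of onsite vertebral imaging will be tabulated by a simple 2*2 contingency table against blinded adjudication". Sensitivity, specificity, PPV, NPV and a likelihood ratio with 95% CIs follow, plus kappa between onsite and blinded readers. Adjudication is also what defines a case in Section 8.1.1: "presence of at least one vertebra classified as grade 1, 2, or 3 semi-quantitatively by Genant's score as agreed by both study radiologists".

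The same paragraph of 8.1.3 then adds a logistic model to "assess the probability of a subject with adjudicated vertebral fracture will have the vertebral fracture as diagnosed onsite". An area under the ROC curve is to "evaluate the degree of discrimination for the probability of interested response". On covariates: "Effects of age, region, and/or other analysis variables will be adjusted in the model whenever statistically appropriate".

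The next paragraph, on screening for osteoporosis, introduces its own model as similar and uses the same sentence form, to "assess the probability of a subject with adjudicated vertebral fracture will have densitometric osteoporosis". Its roles are stated: "An osteoporosis diagnosis in the study will be deemed as 'true condition' whereas the blinded vertebral imaging outcome will be the diagnostic tool".

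Section 8.1 announces a separate SAP. Its text is not in this document, and nothing else in the document defines the onsite model differently.

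**The concern.** In the osteoporosis model the conditioning variable (adjudicated fracture) is the test and the response lies on the side of the condition being diagnosed. In the onsite model the same sentence form puts the reference standard in the conditioning position and the test in the response position. An AUC computed on that response shows how well adjudication and any covariates predict what the site wrote down. It does not show how well the site's reading separates women with and without an adjudicated fracture.

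At stake is one number that would be read as the discrimination of onsite imaging. It would depend on the fracture prevalence in the sample, and that prevalence is partly fixed by the age-stratified sampling (Section 3.5) and not by the readers. The primary and secondary analyses are untouched.

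**Working it through.** **Inputs**
- Prevalence, from the assumed values and cell sizes in Table 8.3.1: (44×5 + 81×7 + 100×12 + 90×16 + 80×20 + 70×23 + 53×37)/518 = 8598/518 = 16.6%. As a check that the table was read correctly, 518/0.95 = 545.3, which agrees with the stated 545 per region.
- Onsite sensitivity (Se) and specificity (Sp): not in the documents. Assumed ranges are Se 0.3 to 0.9 and Sp 0.80 to 0.99.
- The plan states no AUC, so there is no figure of its own to reproduce.

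**Formulas.** With one binary predictor the ROC curve has a single interior point, and AUC = (1 + true-positive rate − false-positive rate)/2.
- Response = adjudicated fracture, predictor = onsite reading: the rates are Se and 1−Sp, so AUC = (Se+Sp)/2.
- Response = onsite reading, predictor = adjudicated fracture (as written, all subjects): the rates are PPV and 1−NPV, so AUC = (PPV+NPV)/2.

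**Worked case, Se 0.70/Sp 0.95, prevalence 0.166**
- True positives 0.166×0.70 = 0.1162; false positives 0.834×0.05 = 0.0417; PPV = 0.1162/0.1579 = 0.736.
- True negatives 0.834×0.95 = 0.7923; false negatives 0.166×0.30 = 0.0498; NPV = 0.7923/0.8421 = 0.941.
- As written: (0.736+0.941)/2 = 0.838. Accuracy AUC: (0.70+0.95)/2 = 0.825.

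**Across the assumed range, prevalence 16.6%, no covariates**

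| Se / Sp | As written | Accuracy AUC | Difference |
|---|---|---|---|
| 0.30 / 0.99 | 0.867 | 0.645 | +0.222 |
| 0.50 / 0.99 | 0.909 | 0.745 | +0.164 |
| 0.50 / 0.95 | 0.785 | 0.725 | +0.060 |
| 0.70 / 0.95 | 0.838 | 0.825 | +0.013 |
| 0.90 / 0.95 | 0.881 | 0.925 | −0.044 |
| 0.70 / 0.90 | 0.760 | 0.800 | −0.040 |
| 0.90 / 0.80 | 0.724 | 0.850 | −0.126 |

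The sign is not fixed, and the order of two readers can reverse: 0.50/0.99 beats 0.90/0.80 as written (0.909 against 0.724) but loses on the accuracy AUC (0.745 against 0.850).

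**Same reader, different prevalence.** At Se 0.70/Sp 0.95 the accuracy AUC stays at 0.825. The as-written AUC is 0.704, 0.807, 0.852 and 0.868 at prevalences of 5%, 12%, 20% and 37%, all of them age-group values in Table 8.3.1.

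**Narrow reading: adjudicated cases only.** Adjudicated status is then constant and the onsite result is only the outcome, so covariates alone drive the AUC. In a simulation of 400,000 subjects with onsite sensitivity unrelated to age, a model with age gave an AUC of 0.50 to 0.51, whether sensitivity was 0.50, 0.70 or 0.90.

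**Covariates in the right direction.** In the same simulation, at Se 0.70/Sp 0.95, adding age to the model with adjudicated fracture as response raised the AUC from about 0.825 to about 0.88. The increase belongs to age, not to the onsite reader.

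**The case against.** The strongest reply is that nothing the objective needs is lost. The 2x2 measures and kappa are correctly oriented and reported with the model. This stands, and it limits the point to one supplementary statistic. A reader might infer that the misdirected AUC would conceal fractures missed onsite. The documents do not support that, because the missed share is 1 − sensitivity and sensitivity is reported directly with its CI.

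A second reply is that the regression is legitimate. This also stands: its fitted probabilities are sensitivity and 1 − specificity, it can show how these vary by age and region, and the unadjusted odds ratio is the same in both directions. To call the whole analysis reversed or invalid would go too far. The fault lies in the AUC attached to it.

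Third, the sentence is ungrammatical and names no dependent variable, so the intended model may differ. The parallel osteoporosis sentence supports the literal reading, but certainty is not needed: the AUC fails as an accuracy measure in all subjects and in adjudicated cases only. The (PPV+NPV)/2 figures apply to the first reading alone, and only without covariates.

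Fourth, the size is uncertain and can be close to nil. That is correct. A reader might be tempted to take onsite sensitivity from Section 1.1, where a quarter to a third of incident radiographic fractures are said to be clinically diagnosed. That share concerns fractures coming to clinical attention, mostly without symptoms. Here every participant is expected to be filmed, so it is no proxy for an onsite reader's sensitivity.

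Finally, a reader might object that the AUCs for the two exploratory objectives run in opposite directions and cannot be compared. No comparison is planned, so nothing rests on this.

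**Conclusion.** The point holds as a minor error. As worded, the AUC for exploratory objective 1 is computed on the onsite diagnosis and does not measure the accuracy of onsite reading under either reading of the sentence. Unadjusted and in all subjects, it departs from the accuracy AUC by about −0.13 to +0.22 over the assumed Se and Sp ranges at 16.6% prevalence, and by about 0.01 at Se 0.70/Sp 0.95. These sizes rest on assumed reader performance and on the planning prevalences in Table 8.3.1; they are not forecasts for the study or for an adjusted model. The identity with (PPV+NPV)/2, and hence the dependence on prevalence, needs no such assumption beyond two binary readings and no covariates.

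**What to change.** In Section 8.1.3 or the separate SAP, name the response and predictor of the model that supplies the AUC: adjudicated vertebral fracture as response, onsite diagnosis as predictor. Report the AUC without covariates as the accuracy measure, noting that it then equals (Se+Sp)/2 and so summarises figures already planned. If an AUC with age, region or other covariates is also reported, label it as including their own predictive value. Keep the regression of onsite diagnosis on adjudicated status only to describe how sensitivity and specificity vary by age and region, with no AUC attached.

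The cost is a sentence or two of text. No data collection, procedure or sample size changes, and Section 8.1 lets changes to exploratory analyses be listed with reasons in the CSR.
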